## **General Considerations**

### **Timing of Analyses**

The final analysis will be performed after all data have been entered and the database has been locked.

### **Analysis Populations**

Analysis population will be all available subjects on an intention-to-treat basis for the outcome measures.

## **Missing Data**

This is an intention to treat study so all non compliers, withdrawn patients or missing data will be analysed by imputation. Missing data will be handled using multiple imputation methods, assuming that the assumption of data missing at random is met. We will also do a completed cases only analysis.

## **Summary of Study Data**

All continuous variables will be summarised using the following descriptive statistics: n (non-missing sample size), number of missing records, mean, standard deviation, median, maximum and minimum. The frequency and percentages (based on the non-missing sample size) of observed levels will be reported for all categorical measures. In general, all data will be listed, sorted by subject and treatment and where appropriate by visit number within subject.

All summary tables will be structured with a column for each treatment in the order (Intervention, Control) and an additional column for the total population relevant to that table/treatment, including any missing observations'

## **Demographic and Baseline Variables**

Baseline characteristics for patients are: Age, gender, colorectal cancer diagnosis, treatment for colorectal cancer (Colon or rectal surgery; laparoscopic or open surgery; Temporary, permanent stoma or no stoma; Chemotherapy or no chemotherapy).

## **Efficacy Analyses**

Scoring for outcomes follows the scoring instructions given for each questionnaire. Where no such instruction is present, the following approach will be taken:

If no more than 20% of questionnaire items are missing, the missing items will be replaced by the mean of the remaining items to build a sum score. Where more than 20% of the items are missing, the sum score will be set to missing.

Data for continuous outcome measures will be assessed for normality prior to analysis. Transformations of the outcome variables will be used where necessary if these are not normally distributed.

Outcomes will be analysed as baseline versus end of intervention (EoI) and baseline versus 3 months after intervention.

Continuous outcome will be using multiple linear regression (i.e. analysis of covariance, ANCOVA). Intervention effect differences will be reported with 95% confidence intervals (CIs) and p-values. The baseline characteristics will be explored for meaningful differences between trial arms. Where these are considered meaningful and important these variables will be entered into a stepwise selection procedure and the primary analysis will be adjusted for these variables if they are statistically selected (usual criteria  $p < 0.05$ ).

Outcome measurements across multiple study visits (baseline, EoI, 3 months) will also be analysed using mixed effects (repeated measures) regression models. Models will include fixed effects for intervention group, time point, and their interaction, plus random effects for each subject to account for repeated measures, and will assume a general covariance structure. Each model will also include fixed effects for baseline values of the outcome, other covariates, in the same way as described above for ANCOVA models.

Ordinal and binary outcomes will be analysed as described above using logistic regression.

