6.2.3 Sample size

As this is a pilot RCT with embedded feasibility study, a formal power calculation is not appropriate; the study is not powered to detect a clinically meaningful difference in the primary outcome between the rehabilitation and usual care groups. Rather the aim is to provide robust estimates of the likely rates of recruitment and retention, and to yield estimates of the variability of the primary and secondary outcomes to inform power calculations for a future large-scale trial. We will therefore use the pilot trial (Phase 2 of the proposed study) in order to provide a quantitative estimate of the intervention impact (relative to control) in order to inform the sample size estimation for a definitive trial. While we recognise that the number of patients to be included in a pilot study will depend on the parameters to be estimated, a general rule of thumb is to take a minimum of 30 patients to estimate a parameter [37], which we believe is achievable

in this study. For the pilot RCT (Phase 2), we believe that over 6 months across the 3 sites we will be able to approach 250 patients. From their responses we will be able to determine whether it is possible to recruit patients and also estimate eligibility, consent, participation and retention rates and speed of recruitment for a future large scale trial. We have conservatively estimated that we will recruit approximately 66 patients. Cancer clinicians estimate that approximately one third will be ineligible (e.g. have advanced disease) and based on recruitment to a RCT about physical activity with cancer patients in Scotland (27% recruitment rate) [50] and a trial involving colorectal cancer patients within 3 months of completing surgery conducted in Canada (35% recruitment rate) [51] we estimate that about a third of eligible patients will consent. Thus, we estimate that in Cardiff and Stirling 26 patients in each site will be recruited (13 intervention group and 13 control group). In Inverness, we estimate that 14 patients will be recruited (7 intervention group and 7 control group). However, a recruitment rate of 71 per cent, which was achieved in a study of a personalised lifestyle programme for colorectal cancer survivors in Scotland [34], would provide a total of 118 patients.

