### **Primary Efficacy Analysis**

The primary outcome is the change in physical activity recorded with accelerometers between baseline and EoI. The variables to be analysed are minutes spent each week on light moderate and vigorous exercise as well as minutes spent sedentary and will be analysed using multiple linear regression. The model will have outcome as the dependent variable with baseline values as a covariate along with intervention group (Intervention/Control), and hospital as fixed effects.

Confounding variables to be assessed for importance are: Cognitive risk perception, Affective risk perception, Physical Activity self-efficacy, age, sex, surgery type (Colon or rectal surgery), Surgical intervention (e.g. laparoscopic or open surgery); stoma (Temporary (a loop ileostomy), permanent stoma or no stoma) and medical intervention (Chemotherapy or no chemotherapy).

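### The SAP checks the outcomes rather than the ANCOVA residuals for normality, so a skewed baseline can prompt a needless transformation that takes the adjusted effect and residual SD off the minutes scale

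*SAP*

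**What the plan says.** The general rule stands in the SAP under Efficacy Analyses: "Data for continuous outcome measures will be assessed for normality prior to analysis". It continues: "Transformations of the outcome variables will be used where necessary if these are not normally distributed". No test or threshold is named. The SAP also does not name a transformation, say how zero or negative values are handled, or give a back-transformation. Residuals are not mentioned.

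Under Primary Efficacy Analysis, "The primary outcome is the change in physical activity recorded with accelerometers between baseline and EoI". The variables are "minutes spent each week on light moderate and vigorous exercise as well as minutes spent sedentary". For the model, "The model will have outcome as the dependent variable with baseline values as a covariate", with arm and hospital as fixed effects. On reporting, Efficacy Analyses adds: "Intervention effect differences will be reported with 95% confidence intervals (CIs) and p-values".

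Three other places bear on the consequences:
- SAP, Summary of Study Data: every continuous variable is "summarised using the following descriptive statistics: n (non-missing sample size), number of missing records, mean, standard deviation, median, maximum and minimum", by arm and in total.
- Protocol 6.2.3, repeated in the SAP under Sample Size: one aim is "to yield estimates of the variability of the primary and secondary outcomes to inform power calculations" for a later trial. Both sections also want a quantitative estimate of the intervention's effect relative to control, for the definitive sample size.
- SAP, Reporting Conventions: parameters not on the raw scale get a rule on significant figures and nothing on returning them to minutes.

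**The concern.** ANCOVA assumes that the errors are roughly normal once baseline, arm and hospital are in the model. It assumes nothing about the distribution of the outcome itself. If baseline activity is skewed and predicts follow-up activity, the follow-up values inherit some of that skew. The model then removes it through the baseline term. A check made on the outcome before fitting sees the skew. A check on the residuals does not. The rule as written is therefore aimed at the wrong quantity.

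At stake is what the pilot hands on. If one of the activity variables is transformed, its adjusted difference, confidence interval and residual SD are on another scale. A back-transformed log difference, for example, is a ratio and not a difference in minutes. Each activity variable could also end up on a different scale, chosen after the data are seen.

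**Working it through.** The plan gives no figure on this point, so there is none to reproduce. Its only design number is the target of about 66 (26 + 26 + 14 by site). The check is a simulation plus one sample-size formula. Skew, slope and correlation are assumptions, shown as ranges.

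**1. Which variable is checked.** The SAP defines the primary outcome as change, but the model has the outcome as dependent variable with baseline as covariate. With baseline in the model and no transformation, follow-up and change give the same arm effect and the same residuals, so a residual check does not depend on this choice. A check on the outcome does, so both versions are shown.

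**2. Simulation A.** n = 66, 4,000 trials per cell. Baseline x is log-normal with median 100 and log-SD σ. Follow-up is y = 20 + r·x + 0.3·SD(x)·arm + e, with e exactly normal and SD(e) = SD(x)·√(1 − r²). Hospital is left out for simplicity. The table gives the percentage of trials in which Shapiro-Wilk rejects at 0.05.

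| σ | r | follow-up | change | residuals |
|---|---|---|---|---|
| 0.3 | 0.3 | 4.6 | 9.9 | 5.0 |
| 0.3 | 0.5 | 8.0 | 6.8 | 5.2 |
| 0.3 | 0.7 | 14.8 | 5.6 | 5.0 |
| 0.5 | 0.3 | 5.0 | 17.6 | 4.4 |
| 0.5 | 0.5 | 9.2 | 10.8 | 5.1 |
| 0.5 | 0.7 | 30.5 | 7.1 | 5.7 |
| 0.8 | 0.3 | 7.5 | 30.3 | 5.3 |
| 0.8 | 0.5 | 19.7 | 19.4 | 4.5 |
| 0.8 | 0.7 | 47.4 | 10.5 | 4.6 |

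Follow-up is flagged in about 5% to 47%, change in about 6% to 30%, and residuals at the nominal rate throughout. As r rises, the flag rate goes up for follow-up and down for change, so the verdict of an outcome check depends on a definition that the SAP leaves open. At n = 50 the pattern is the same (follow-up about 5% to 40%).

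**3. Simulation B, reaching higher correlations.** n = 56 (the plan's recruitment assumptions give 250 × 2/3 × 1/3 = 55.6), 1,000 trials per cell. y = 60 + b·x + 20·arm + N(0, 40), with x log-normal and log-SD 0.7. The table gives the percentage of trials in which follow-up is flagged.

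| median x (minutes) | b = 0.4 | b = 0.6 | b = 0.8 |
|---|---|---|---|
| 60 | 17 | 35 | 54 |
| 80 | 27 | 51 | 72 |
| 120 | 51 | 79 | 89 |

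The implied correlations are about 0.49 to 0.73 at a median of 60, and 0.74, 0.85 and 0.91 at a median of 120. Residuals are flagged in 4% to 6%. Change is flagged in 5% to 35% at a median of 60, and in up to 75% over medians of 60 to 120.

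**4. What the raw SD costs in planning.** For an ANCOVA, residual SD = SD·√(1 − r²), so N planned on the raw SD is too large by 1/(1 − r²):
- r = 0.3: 1/(1 − 0.09) = 1.10
- r = 0.5: 1/(1 − 0.25) = 1.33
- r = 0.7: 1/(1 − 0.49) = 1.96

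Take an assumed standardised effect d = 0.5, with 80% power and two-sided 5%. Then n per arm = 2(1.960 + 0.842)²/0.5² = 62.8, so 63. Multiplied by (1 − r²) this is 57.1, 47.1 and 32.02, so 58, 48 and 33 per arm.

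**The case against.** The other side has five fair arguments.

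- **The rule is discretionary.** It applies only where necessary and names no test. A careful analyst might look at residuals anyway. This stands: a reader might infer that skewed baselines will force a transformation, and the SAP does not say so. It nowhere makes the baseline distribution decisive. But the text still names the outcome as the thing checked, and the time as before the analysis.
- **The simulation imposes normal errors**, so every transformation in it is needless by construction. Real activity minutes may leave skewed or uneven residuals, and a transformation may then be justified. This stands: the figures are false-alarm rates, not the share of real trials in which the rule would go wrong. A residual check is also the one that would look for that case directly.
- **The high rates need strong correlations.** The 51% to 89% row rests on a median of 120 minutes and r of 0.74 to 0.91, which nothing in the documents supports. At weaker skew and correlation the outcome is flagged at close to the nominal 5%.
- **The SD in minutes is not lost.** A reader might infer that it is, but Summary of Study Data requires raw means and SDs by arm, and protocol 6.8 says that descriptive presentations will inform the sample size. If the SD of change is tabulated for the same patients, r can even be recovered from the three SDs. This stands. Planning on the raw SD also errs towards a larger trial, not an underpowered one. What the plan does not require is the adjusted difference in minutes, the residual SD or the correlation.
- **No log is specified**, so trouble with zero vigorous minutes or negative changes is only a possibility. The gap is that no transformation and no handling of such values is named.

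**Conclusion.** The point holds in a limited form. The SAP states a rule that checks the wrong quantity for its own primary model. With exactly normal errors and an assumed Shapiro-Wilk test at 0.05, that check flags the follow-up outcome in about 5% to 90% of trials, depending on skew and correlation, and the residuals in about 5%. The width of that range reflects what the documents leave unstated, so the conclusion is that a needless transformation can happen, not that it will.

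If it does, the baseline-adjusted difference, its confidence interval and the residual SD leave the minutes scale. The raw SD and the crude means by arm remain, so the stronger reading, that the pilot would lose its variability estimate, is not supported. The practical cost is a definitive sample size that is 1.10 to 1.96 times what an ANCOVA needs, for r from 0.3 to 0.7, and no planned adjusted effect in minutes. The feasibility objectives are untouched.

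**What to change.** Replace the two SAP sentences on normality and transformation with: *Model assumptions will be checked on the residuals of the fitted ANCOVA. If a transformation is used, the adjusted difference in minutes with a robust or bootstrap 95% CI will also be reported.* For outcomes not measured in minutes, read original units.

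Add that the residual SD in minutes, or the baseline to follow-up correlation, will always be reported for each activity variable.

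Which scale is the main one when residuals are clearly skewed is open to judgement. A pre-named transformation with a stated back-transformation would also be acceptable, provided that the minutes-scale result is given beside it.

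The cost is a few SAP sentences and slightly more output. No new data are needed.

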## **Randomisation and Blinding**

Patients were randomised to the intervention or control group after they consented to participating in the study and after baseline primary and secondary measures were collected. Randomisation with stratification by centre was conducted by Tayside Clinical Trials Unit. Due to the nature of the intervention, the trial was not blinded.

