### **Secondary Efficacy Analyses**

- SPAQ: All minutes of activity during the previous week will be summed up for analysis to provide a total minutes of activity in a week. In addition, the activities will be summed up separately for each week and analysed... Where no entries were made for a day, it will be assumed that there was no activity (0 minutes) in this category.
- FACT-C: The questionnaire consists of 5 subscales (Physical Well-being (PWB), Social/Family Well-being (SWB), Emotional Well-being (EWB), Functional Well-being (FWB), Additional Concerns (AC)). Composite scales are also calculated as described in the guidelines. As emotional well-being was not collected in this trial, composite scores including those questions were not created.
- FACIT-F: The questionnaire consists of 13 items and will be calculated as described in the guidelines.
- Activity Self-efficacy: If no more than 20% of the items are missing, a sum score will be created from all items in the questionnaire and used for analysis.

- EQ-5D: Physical domains will be analysed separately using logistic regression as described above. The health state will be analysed using ANCOVA as described above. In addition, the health utility score will be created and analysed.
- HADS: Two separate scores for anxiety and depression will be created and analysed.
- Risk perception: Three distinct scores will be created: Cognitive risk perception, affective risk perception and perceived severity as a sum of 2 questions each. Each score will only be created if both items are present. Scores will be analysed as described.
- Service use: This data will be analysed by the health economics team and is not part of this SAP.

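### Primary-analysis covariates are picked by a look at baseline imbalance with no threshold and then by stepwise selection, so the model depends on the analyst; hospital is named only in the primary model

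*SAP*

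**What the plan says.** The rule has two stages, both in the SAP under Efficacy Analyses. First, "The baseline characteristics will be explored for meaningful differences between trial arms". Second, for those judged to matter, "these variables will be entered into a stepwise selection procedure and the primary analysis will be adjusted for these variables" when they reach p<0.05. Results are then given in the usual form: "Intervention effect differences will be reported with 95% confidence intervals (CIs) and p-values".

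Primary Efficacy Analysis fixes part of the model: "baseline values as a covariate along with intervention group (Intervention/Control), and hospital as fixed effects". It then lists nine candidates, beginning "Confounding variables to be assessed for importance are: Cognitive risk perception, Affective risk perception, Physical Activity self-efficacy, age, sex, surgery type" and continuing with surgical approach, stoma and chemotherapy.

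On the stratum, Randomisation and Blinding says "Randomisation with stratification by centre was conducted by Tayside Clinical Trials Unit", and that the trial was not blinded. Hospital appears as a model term only in the primary model. The general ANCOVA, mixed-model and logistic descriptions in Efficacy Analyses do not name it. Secondary Efficacy Analyses mostly refers back, for example "The health state will be analysed using ANCOVA as described above".

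**The concern.** In a randomised comparison, baseline differences between arms arise by chance. Screening on them does not identify the covariates worth adjusting for: a strongly prognostic variable that happens to be balanced never enters, while an imbalanced one gets a chance to.

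The SAP does not say how large a difference counts, who decides, or whether selection runs forward or backward. Three further gaps add to this:

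- The characteristics listed under Demographic and Baseline Variables omit risk perception and self-efficacy, yet both are candidates in the primary analysis. It is unclear whether the imbalance screen applies to them.
- Missing Data calls for multiple imputation plus a complete-case analysis. No rule covers imputed datasets that select different variables, or says whether the two analyses share one model.
- Selection can give different covariates for each of the four accelerometer variables, for each secondary outcome, and at each of the two follow-up times.

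Two statisticians could follow this SAP faithfully and report different primary estimates. That matters even in a pilot, because both Sample Size sections say that the trial will supply a quantitative estimate of intervention impact to inform the definitive trial's sample size.

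On the stratum, the programme differs by site in number of weeks, classes per week and session length. Whether each model contains hospital should not be left to interpretation.

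**Working it through.** **Plan's own figure.** The SAP gives no number for this rule, so there is none to reproduce. The planned size is 66 (26 + 26 + 14 by site), or 33 per arm. The SAP's own recruitment fractions give 250 × 2/3 × 1/3 = 55.6, about 28 per arm. That gap is a separate matter; 28 serves here only as a second value.

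**How often chance would trigger a screen.** Assume a cut-off of 0.25 SD and independent, roughly normal candidates. The standardised difference has standard error √(2/n).

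- n = 33 per arm: √(2/33) = 0.246; P(|difference| > 0.25) = 0.31; expected 9 × 0.31 = 2.8 variables; at least one in 96% of trials.
- n = 28 per arm: √(2/28) = 0.267; P = 0.35; expected 9 × 0.35 = 3.1; at least one: 1 − 0.65⁹ = 98%.

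**What the rule does to the analysis.** Simulation of 3,000 trials per setting with no treatment effect. Baseline, arm and site are forced. There are nine candidates (four continuous, four binary, one three-level) and bidirectional stepwise selection at p<0.05. Assumptions, because the SAP gives no values: the screen (none, 0.25 or 0.50 SD); candidates explaining 0% or 20% of residual variance; N = 66, or N = 42 after loss. The fixed model contains the forced terms only and uses the same data. Monte Carlo error on coverage is about 0.4 points.

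| N | Variance explained | Screen | Any covariate selected | Coverage, SAP rule | Coverage, fixed model | Residual SD, SAP rule |
|---|---|---|---|---|---|---|
| 66 | 0% | none | 37% | 93.1% | 94.0% | 0.981 |
| 66 | 0% | 0.25 | 13% | 95.0% | 95.2% | 0.995 |
| 66 | 0% | 0.50 | 2% | 94.8% | 94.9% | 0.999 |
| 66 | 20% | none | 93% | 93.4% | 95.2% | 0.892 |
| 66 | 20% | 0.25 | 46% | 95.1% | 95.4% | 0.970 |
| 66 | 20% | 0.50 | 8% | 95.2% | 95.1% | 0.995 |
| 42 | 0% | none | 38% | 93.8% | 95.2% | 0.968 |
| 42 | 0% | 0.25 | 19% | 94.7% | 95.4% | 0.989 |
| 42 | 0% | 0.50 | 6% | 95.0% | 95.5% | 0.995 |
| 42 | 20% | none | 80% | 92.1% | 94.6% | 0.893 |
| 42 | 20% | 0.25 | 46% | 94.5% | 94.7% | 0.953 |
| 42 | 20% | 0.50 | 13% | 94.9% | 95.1% | 0.989 |

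The true residual SD is 1.000 in the 0% rows. In the 20% rows the fully adjusted value is √(1 − 0.2) = 0.894.

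**Reading the table.**

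- *Dependence on the screen.* At N = 66 with prognostic candidates, the same SAP text leads to adjustment in 93%, 46% or 8% of trials, depending only on a threshold it does not state.
- *Coverage.* With a 0.25 or 0.50 screen it is 94.5% to 95.2%, against 94.0% to 95.5% for the fixed model across all settings. With no effective screen it is 92.1% to 93.8%.
- *Residual SD.* With useless candidates it is 1.9% (N = 66) or 3.2% (N = 42) low without a screen, and at most 1.1% low with one. With prognostic candidates, the screened SD (0.953 to 0.995) lies above 0.894.

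A separate run (4,000 trials per setting, 66 or 56 patients) gave type I error of 5.2% to 6.0% at a 0.25 screen and 4.8% to 5.1% at 0.50, against 4.5% to 5.3% for the fixed model. Any inflation is therefore about one point at most at the looser screen.

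**The case against.** The strongest reply is that the plan is more constrained than it looks. Baseline value, arm, hospital and the nine candidates are all named in advance, the procedure is openly described, and four of the candidates are already clinical confounding factors in the protocol (section 6.5.4). The study is a pilot without a power calculation, and no decision rests on these p-values. All of this stands, and it limits the seriousness of the point. It does not make the final model reproducible.

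Three stronger readings are tempting, and the documents do not support them:

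- *That intervals and residual SDs will be too small.* This is a known consequence of unrestricted stepwise selection. The SAP screens first, and under plausible screens the effect is close to nil. With prognostic candidates the SD errs upward relative to full adjustment.
- *That the definitive trial would be undersized as a result.* Neither document says the model's residual SD will be carried forward. Protocol section 6.8 refers to descriptive presentations of the outcomes, and the SAP's Summary of Study Data reports raw SDs by arm, which covariate selection cannot change.
- *That the stratum is left out of the other analyses.* The secondary section follows the primary model, and its back-reference can be read as bringing hospital along. For the secondary ANCOVAs this is an ambiguity. The mixed-model and logistic descriptions come before the primary model and do not name hospital, so there the gap is plainer.

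A minimal fixed model also has a cost, because it forgoes precision if an omitted covariate is prognostic. In the simulated 20% case the residual SD is 1.000 rather than 0.894.

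**Conclusion.** The point holds as one about prespecification. Covariates enter the primary analysis through a between-arm look without a threshold and then stepwise selection, in an unblinded trial. The model is therefore not determined by the SAP, may vary across outcomes and time points, and is steered by chance imbalance.

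The numerical consequence is small and cannot be pinned down, because it turns on the missing threshold. It is negligible at assumed screens of 0.25 to 0.50 SD. At worst, coverage is about 92% to 94%, with the SD 2% to 3% low for useless candidates, if nothing is screened out. These figures rest on assumed screens, covariate distributions, prognostic strength and loss to follow-up. The finding about hospital is part ambiguity (secondary ANCOVAs) and part omission of a named term (mixed and logistic models). The change is worth making, but the defect does not undermine the pilot's main objectives.

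**What to change.** Amend the SAP before data by arm are examined:

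1. Delete the imbalance screen and the stepwise step.
2. For every continuous outcome, prespecify a model with the baseline value of that outcome, arm and hospital.
3. Add hospital to the mixed models, which already contain arm, and to the logistic models where cell counts allow.
4. If more adjustment is wanted, name a small number of prognostic covariates now, on clinical grounds, and use the same set for every outcome.
5. Show the remaining listed variables descriptively by arm.
6. State which SD will be passed to the definitive trial; the descriptive SDs already planned are one candidate.

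The cost is a few sentences of SAP text and less analysis work, and the same model can be fitted to each imputed dataset. There are two downsides. Some precision is lost if a strongly prognostic covariate is left out, which naming it in advance reduces. Cells may also be sparse in the logistic models at the smallest site, planned at 14 patients, so the SAP should say what happens if hospital cannot be fitted there.

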## **Technical Details**

All analysis will be performed using SAS 9.3. All data, analysis programs and output will be kept on the Mackenzie Server and backed up according to the internal IT SOPs.

Analysis programs will be required to run without errors or warnings. The analysis programs for outcomes will be reviewed by a second statistician, and any irregularities within the programs will be investigated and fixed and date of finalised analysis programs will be signed and recorded.

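### The SAP's supplementary repeated-measures model uses baseline both as a response visit and as a covariate; it is degenerate under an unstructured covariance, while the ANCOVAs are unaffected

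*SAP*

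**What the plan says.** The SAP's Efficacy Analyses section first sets out ANCOVA for continuous outcomes, at end of intervention (EoI) and at 3 months after it. It then adds a second model: "Outcome measurements across multiple study visits (baseline, EoI, 3 months) will also be analysed using mixed effects (repeated measures) regression models". Three further statements define that model:

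- Fixed effects: "Models will include fixed effects for intervention group, time point, and their interaction".
- Within-subject part: "plus random effects for each subject to account for repeated measures, and will assume a general covariance structure".
- Baseline: "Each model will also include fixed effects for baseline values of the outcome, other covariates", to be handled as in the ANCOVA models.

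Nothing in Efficacy Analyses, Primary Efficacy Analysis or Secondary Efficacy Analyses limits the responses to the follow-up visits, or says which of the two devices carries the within-subject correlation.

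The primary model is separate and uses baseline once: "The model will have outcome as the dependent variable with baseline values as a covariate along with intervention group", with hospital also as a fixed effect. Technical Details adds: "Analysis programs will be required to run without errors or warnings".

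**The concern.** At the baseline visit the response and the covariate are the same number. A regression that contains those rows can predict them perfectly, so they say nothing about the intervention but do affect the slope and the variance estimate. The subject random effect and the general covariance also do the same job twice.

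At stake are the longitudinal estimates for the continuous outcomes. The SAP's Sample Size section says that the pilot should give estimates of outcome variability and of intervention impact for planning the definitive trial. A model that deflates the residual variance, or that the analyst must replace with an unspecified one in an unblinded trial, serves that purpose poorly.

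**Working it through.** The documents give no figure for this model, so there is none to reproduce. The check is algebra plus simulation.

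**Inputs.** From the SAP: N = 66 (14 + 26 + 26 by site), 1:1 within site, three visits, and hospital as a fixed effect. Assumed, because the documents give no values: SD 1 at each visit (also 1.3 at follow-up), correlation 0.3 to 0.7, exchangeable or AR(1), no true effect, no missing data. There were 1,500 simulated trials per scenario, so the Monte Carlo standard error of a coverage near 0.90 is √(0.9 × 0.1 / 1500) ≈ 0.008.

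**1. Unstructured 3x3 covariance.** Let x be the baseline value and β its slope. With β = 1 and no baseline time, group or hospital effect, every baseline residual is zero. If the baseline residual variance is v, those rows add −(66/2) × ln v to the log-likelihood, which grows without limit as v falls. Moving v from 10⁻⁴ to 10⁻⁸ should add 33 × ln(10⁴) = 303.9; the evaluated log-likelihood went from 78.0 to 382.0. In an iterated maximum-likelihood fit to one simulated data set:

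| Step | Slope | Baseline residual variance | Log-likelihood |
|---|---|---|---|
| 0 | 0.633 | 0.113 | −166.2 |
| 1 | 0.831 | 0.024 | −114.7 |
| 5 | 0.993 | 4.7 × 10⁻⁵ | 90.9 |
| 20 | 1.000 | 3.3 × 10⁻¹⁵ | 861.9 |

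**2. What the limit estimates.** A slope of 1 is a change-score analysis. The standard error of a difference between two arms of 33 with SD 1 is 2/√66 = 0.246. At correlation ρ = 0.5:

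- change score: 0.246 × √(2(1 − ρ)) = 0.246
- ANCOVA: 0.246 × √(1 − ρ²) = 0.213

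The simulated mean standard errors are 0.245 and 0.215, a ratio of 1.14.

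**3. Random intercept on top of an unstructured covariance.** The marginal covariance is the residual matrix plus a constant in every cell. That constant can be moved freely between the two parts, so the intercept variance is not identifiable. The marginal covariance does not change when it moves, and so neither do the fixed effects or their standard errors.

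**4. Random intercept only.** Take exchangeable ρ = 0.5. The pooled slope is roughly (1 + 0.5 + 0.5)/3 = 0.667. The residual variance is then (1 − 0.667)² = 0.111 at baseline and 1 − 2(0.667)(0.5) + 0.667² = 0.778 at each follow-up visit. The model averages the three: (0.111 + 0.778 + 0.778)/3 = 0.556. Its standard error is 0.246 × √0.556 = 0.184, against a true 0.246 × √0.778 = 0.217, so it is about 15% too small. The simulation agrees:

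| True structure | Model SE, EoI group difference | Empirical SE | Ratio | Coverage, EoI group difference | Coverage, EoI minus baseline contrast |
|---|---|---|---|---|---|
| Exchangeable 0.3 | 0.208 | 0.244 | 0.85 | 0.910 | 0.947 |
| Exchangeable 0.5 | 0.184 | 0.216 | 0.85 | 0.900 | 0.955 |
| Exchangeable 0.7 | 0.147 | 0.176 | 0.84 | 0.905 | 0.955 |
| Exchangeable 0.5, follow-up SD 1.3 | 0.230 | 0.273 | 0.84 | 0.902 | 0.970 |
| AR(1) 0.5 | 0.200 | 0.215 | 0.93 | 0.925 | 0.962 |
| AR(1) 0.7 | 0.168 | 0.175 | 0.96 | 0.942 | 0.967 |

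A separate run at N = 66 covered 0.91 at EoI and 0.89 to 0.91 at 3 months under exchangeable correlation 0.5 to 0.7. Under AR(1) 0.5 it covered 0.948 at EoI but 0.882 at 3 months.

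**5. Limit of the last column.** It concerns EoI minus baseline only. Under AR(1) 0.5 the correlation between baseline and 3 months is 0.25, so the true standard error of the 3-month contrast is 0.246 × √(2 × 0.75) = 0.302. With complete data the model assigns both follow-up contrasts the same standard error, 0.265 in that scenario. The ratio is 0.265/0.302 = 0.88, so this contrast is not protected there.

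**6. After the fix.** With EoI and 3 months as the only responses, baseline as covariate and an unstructured 2x2 covariance, coverage at EoI is 0.945 to 0.959 over the same scenarios. At exchangeable 0.5 the mean standard error is 0.218 against a true 0.212. ANCOVA gives 0.215 against 0.213, with coverage 0.953.

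**The case against.** The best defence has five parts.

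- **The model is supplementary.** ANCOVA covers both EoI and 3 months, so no time point depends on this model alone. This stands and sets the severity.
- **The study is an unpowered pilot.** Outcome SDs for planning can come from the descriptive summaries and the ANCOVAs. This also stands. The longitudinal estimates would still be reported, and the SAP says "Intervention effect differences will be reported with 95% confidence intervals (CIs) and p-values".
- **The SAP frames outcomes as baseline versus follow-up.** That points to the group-by-time contrast, whose coverage is nominal or conservative for EoI minus baseline. This stands for that contrast, at the price of a larger standard error than ANCOVA (0.245 against 0.213 at exchangeable 0.5). It does not carry over to 3 months under AR(1).
- **The wording is loose.** The general covariance is not defined, and tying the covariates to the ANCOVA models suggests that follow-up responses may have been meant. That is possible, but the text names baseline as an analysed visit and the cross-reference does not remove it.
- **There is a quality check.** A second statistician reviews the outcome programs and irregularities are to be fixed. A diverging fit might well be caught, but the SAP does not say what would replace the model.

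A reader might infer that the model cannot run at all under the SAP's rule on errors and warnings. The divergence was shown by algebra and purpose-written fitting code, not in SAS 9.3, so what that software would report is not established.

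**Conclusion.** The specification is wrong as written, and the fault is confined to a secondary model. Read with an unstructured covariance it has no maximum-likelihood solution, and its limit is a change-score analysis about 14% less precise than ANCOVA at ρ = 0.5. Read as random intercept only, standard errors for the follow-up group differences are about 15% too small, with coverage of about 89% to 91% under exchangeable correlation 0.5 to 0.7. Under AR(1) coverage is about 0.93 to 0.95 at EoI and about 0.88 at 3 months (correlation 0.5). These sizes rest on assumed correlations and variances and on complete data; the unbounded likelihood rests only on the unstructured reading.

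Three stronger readings are not supported. The trial's main result is not compromised, because the primary and 3-month ANCOVAs use baseline only as a covariate. Not every interval from the model is too narrow, because the EoI-minus-baseline contrast keeps its coverage. The redundant random intercept does not by itself bias the effects or their standard errors. The correction should be made, but it is not a condition for the primary analysis.

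**What to change.** Replace the model description in the SAP's Efficacy Analyses with one of these:

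- **Follow-up visits only as responses (EoI and 3 months).** Fixed effects: group, time, group x time, baseline value, baseline x time, and hospital. Use an unstructured 2x2 within-subject covariance and no separate random intercept.
- **All three visits as responses.** Constrain the arms to a common baseline mean, drop the baseline covariate, and use a single covariance device.

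Either is acceptable. The SAP should name one before analysis, together with the contrast to be reported at each visit. The cost is two sentences, with no new data and no material programming work.
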